2. ABSTRACT

Rationale: Guideline recommended evidence-based clinical care correlates with improved patient outcomes. In real life care, however, adherence to guideline recommendations remains suboptimal. In real life, patients may receive suboptimal treatment and as a result treatment targets are not always met. To support and improve secondary prevention for cardiovascular disease, PENELOPE and PENELOPE-CTRL are designed to support guideline implementation on lipid management and provide valuable feedback to care-givers on real world data.

The recent PENELOPE study was designed to determine the effect of a protocolized, Dutch-, and European Society of Cardiology (ESC) guidelines based strategy of stepwise intensified lipid management in patients at very high risk for Acute coronary syndrome (ACS). In PENELOPE 22 Dutch non-academic hospitals, members of the WCN investigator network, implemented a protocol guided guideline approach in a consecutive cohort of very high-risk patients admitted for ACS over the period 01-01-2019 to 31-08-2020. Lipid values and medication strategy are collected at baseline (index ACS), and after three months and one year post ACS, in order to establish the percentage of patients on target Low density lipoprotein cholesterol (LDL-C).

The current PENELOPE-CTRL study on the other hand, is designed to serve as a contemporary control cohort for PENELOPE. PENELOPE-CTRL is a retrospective observational study, creating a contemporary snapshot of real-life lipid management for secondary prevention in very high-risk patients. PENELOPE-CTRL will collect data in similar hospitals who did not participate in the PENELOPE trial.

To allow comparison of these two strategies, protocol guided versus real life implementation of the cholesterol treatment guidelines, both cohorts include similar patients, and similar data will be collected (e.g., lipid lowering drugs, lipid panels) . Analysis will be done at similar time points. Comparing the real-life data from PENELOPE-CTRL with the data from the PENELOPE study will quantify the effect of a strategy of protocolized guideline-based lipid management with regards to the incidence of target LDL-C levels in very high-risk patients, 3 months and one year after hospitalisation with a myocardial infarction.

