3. INTRODUCTION AND RATIONALE

One of the main underlying causes of atherosclerotic cardiovascular disease is the retention of LDL-C and other cholesterol containing lipoproteins within the arterial wall. There is an approximately linear relationship between the absolute reduction in LDL-C and the proportional reductions in the incidence of coronary and major vascular events.[1] Clinical trials have clearly shown that the lower the achieved LDL-C values, the lower the risk of future cardiovascular events. Guidelines summarize and evaluate available evidence with the aim of assisting health professionals in proposing the best management strategies for an individual patient with a given condition.[2, 3] For secondary prevention in very-high-risk patients the 2016 ESC Guidelines for the management of dyslipidaemia recommended an LDL-C reduction to <1.8 mmol/l.[1] in the 2019 ESC Guidelines this was narrowed down even further to <50% from baseline and an LDL-C goal of <1.4 mmol/L.[4] If the LDL-C goal is not achieved 4 - 6 weeks after the cardiovascular event (CVE) despite maximal tolerated statin therapy, ezetimibe should be added first, followed by Proprotein convertase subtilisin/kexin type 9 inhibitors (PCSK9-i). [3] The Dutch Cardiovascular Risk Management (CVRM) guideline (in the period PENELOPE was performed) recommends an LDL-C goal of at least <1.8 mmol/L for very high-risk CV-patients.

Adherence to treatment guidelines is a predictor of fewer CV hospitalizations. In real life care, however, compliance to guidelines for secondary prevention of cardiovascular disease, can be improved according to recent European and Swedish national studies. [5-8] A strategy of protocolized, Dutch- and ESC-guideline based stepwise approach in lipid lowering therapy (LLT) to reach target LDL-C in very high-risk patients was studied in the PENELOPE study. Protocolized LLT consisted of 3 steps, with LDL-C levels measured \geq 4 weeks after each step:

- Step 1: if at baseline LDL-C >1.8 mmol/L, then a high intensity statin (HIST), defined as atorvastatin \geq 40 mg OD or rosuvastatin \geq 20 mg OD, had to be initiated.
- Step 2: if \geq 4 weeks after step (1) LDL-C >1.8 mmol/L, then ezetimibe 10 mg OD had to be initiated.
- Step 3: if \geq 4 weeks after step (2) LDL-C >1.8 mmol/L alirocumab had to be initiated following pre-specified criteria:
 - if LDL-C 1.8-2.6 mmol/L, addition and dosing of alirocumab was left at the investigator's discretion

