7. DATA COLLECTION

The following data will be collected from the local electronic health record starting at admission up to 18 months:

- Baseline characteristics including at least age at admission, index event, medical history and cardiovascular risk factors
- Lipid lowering medication, including start and stop dates, (perceived) cause of interruption or intolerance, and dosage
- Lipid panels: all available total cholesterol, LDL, HDL, and TG values will be collected
- Clinical course, including death, myocardial infarction, stroke and (urgent) revascularisation and co-medication

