8. STUDY OUTCOMES

a. PRIMARY STUDY OUTCOME

The primary outcome is defined as the cumulative incidence of patients reaching the LDL-C target level (≤ 1.8 mmol/L) after admission for a type I (N)STEMI with oral lipid lowering medication only, compared to the designated PENELOPE cohort.

Further details on handling of missing or out of window values collected from regular care will be detailed in the endpoint charter, used for endpoint adjudication.

After analysis of the PENELOPE CTRL data the CTRL cohort will be compared to the original PENELOPE cohort.

b. SECONDARY STUDY OUTCOMES

- a) Mean time of reaching the primary outcome, compared to the designated PENELOPE cohort.
- b) Cumulative incidence of patients reaching the LDL-C target level (≤ 1.8 mmol/L) within 90 days after admission for a type I (N)STEMI with oral lipid lowering medication only. This outcome will be estimated with two analysis:
 - only including patients reaching (at least once) LDL-C target within 90 days (without using LDL-C measurements after this window) and
 - additionally including the first available LDL-C measurement (at least 14 days) after the last modification in oral lipid lowering therapy within 90 days after baseline (even if this measurement is after 90 days). This way CTRL mimics the original PENELOPE dataset, where LDL measurement 4-6 weeks after a drug regimen change was mandatory to establish the treatment effect, and this measurement also includes the effect of the last drug regimen change within 90 days.

- c) Cumulative incidence of patients reaching other LDL-C target levels (e.g. ≤ 1.4 mmol/L and 50% LDL-C reduction compared to baseline) and mean LDL-C levels with only oral medication after admission for a type I (N)STEMI, compared to the designated PENELOPE cohort.
- d) Cumulative incidence of reaching LDL-C target levels (≤ 1.8 mmol/L, ≤ 1.4 mmol/L and 50% LDL-C reduction) compared to baseline) and mean LDL-C levels with any lipid lowering drugs (so including the effects of PCSK9i), compared to the designated PENELOPE cohort.
- e) Cumulative incidence of patients reaching LDL-C target levels with only (i) high-intensive statin (compared to cum. effect after STEP 1 in PENELOPE) or (ii) high-intensive statin and/or ezetimibe (compared to cum. effect after STEP 2 in PENELOPE).

c. STUDY PROCEDURES

As PENELOPE-Control is a retrospective cohort registration there are no study procedures.

d. Randomisation, blinding and treatment allocation

Not applicable.

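### Secondary outcome a compares mean time to LDL-C target between cohorts with different blood-test calendars, so test timing alone can produce a difference, of unknown size and direction

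*Protocol*

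**What the plan says.** Section 8a: "The primary outcome is defined as the cumulative incidence of patients reaching the LDL-C target level", meaning ≤1.8 mmol/L on oral therapy only. No time window is attached. Section 8b a) then asks for "Mean time of reaching the primary outcome, compared to the designated PENELOPE cohort". It gives no event date, censoring rule or estimator.

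On testing in PENELOPE, section 3 says "Protocolized LLT consisted of 3 steps, with LDL-C levels measured" at least 4 weeks after each step. Section 8b b) describes PENELOPE as a dataset "where LDL measurement 4-6 weeks after a drug regimen change was mandatory to establish the treatment effect". The abstract adds "Lipid values and medication strategy are collected at baseline (index ACS), and after three months and one year post ACS", which leaves open which PENELOPE values enter the comparison.

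On testing in CTRL, section 8c says "As PENELOPE-Control is a retrospective cohort registration there are no study procedures". Section 7 says "Lipid panels: all available total cholesterol, LDL, HDL, and TG values will be collected", under the lead-in "The following data will be collected from the local electronic health record starting at admission up to 18 months". No routine-care test interval is stated anywhere.

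Outcome b has a second analysis that admits a later first test after the last therapy change, expressly so that CTRL resembles PENELOPE. Outcome a has no counterpart.

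**The concern.** The day on which LDL-C crosses 1.8 mmol/L is never observed. It lies between the last test above target (or admission) and the first test at or below it, so the times are interval-censored. A plain mean needs one date per patient, and the natural choice is the first on-target test. The lag from crossing to detection is then set by protocol in PENELOPE and by local habit in CTRL. It is tied to cohort, which is the comparison itself.

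For example, suppose two patients both cross at day 21. One is tested at day 35 and scores 35. The other is tested at day 90 and scores 90. The 55-day gap is all detection lag.

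A gap in outcome a would naturally be read as protocolized care bringing LDL-C to target sooner, and section 13j foresees use of the results with health authorities and insurers. The propensity-score methods in section 10 address baseline imbalance and cannot repair a mismeasured time. The endpoint charter is assigned missing and out-of-window values, and a routine on-target test at day 90 need be neither.

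This is separate from the effect of test frequency on the proportion at target and from the lack of a value for non-reachers. It remains with equal incidence and reachers only.

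**Working it through.** The protocol states no expected time, power or alpha for this outcome, so there is no figure to reproduce. The check asks what first-test means show when the true LDL-C course is the same in both cohorts.

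**Inputs.** From the protocol: N=663 for PENELOPE aged ≤70 (section 6a), 700-1200 CTRL candidates (section 6d), and PENELOPE tests 4-6 weeks after a regimen change (section 8b b). Assumed: 70% ever reach target, the crossing times, and every CTRL test date.

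**1. One therapy step.** True crossing is at day 10-28 in both cohorts. The earliest test considered is day 28, so every reacher is first recorded at the first test, and the recorded mean equals the mean first-test date. With dates uniform over the window, PENELOPE has (28+42)/2 = 35 days.

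| CTRL first test | Mean date (days) | CTRL − PENELOPE | Simulated |
|---|---|---|---|
| 4-6 weeks | (28+42)/2 = 35 | 0 | 0.0 |
| 4-10 weeks | (28+70)/2 = 49 | +14 | +13.9 |
| 6-12 weeks | (42+84)/2 = 63 | +28 | +28.0 |
| 8-16 weeks | (56+112)/2 = 84 | +49 | +49.0 |
| 4-26 weeks | (28+182)/2 = 105 | +70 | +70.0 |

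In 60 runs per scenario, with 663 against 700 and against 1200, a Welch t-test rejected at p<0.05 in 2-3% of runs for equal calendars and in 100% for the other four. Proportions at target differed by at most 0.6 percentage points.

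**2. Two therapy steps.** Here 45% cross at day 10-28 and a further 25% at day 52-70, with 663 against 700. The gaps were +0.1 days (same calendar), +28.3 (first CTRL test at 6-12 weeks), +38.1 (8-16 weeks), +63.0 (4-26 weeks) and +2.2 (2-4 weeks).

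**3. Spread-out crossing times, and the sign.** True times among reachers are Weibull (shape 1.3, scale 45 days; mean 41.6 days) in both cohorts. PENELOPE tests near days 35/77/119/365 give a recorded mean of about 69 days.

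| CTRL tests near days | Recorded mean | CTRL − PENELOPE |
|---|---|---|
| 60/120/200/365 | 81 | +11.0 |
| 14/42/180/365 | 95 | +25.9 |
| 42/180/365 | 101 | +32.0 |
| 90/180/365 | 102 | +33.2 |
| 28/60/90/180/365 | about 65 | about −4 |

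The first four gaps come from unrounded means. The last row shows that a denser routine calendar reverses the sign. If PENELOPE contributed only values near days 90 and 365, as the abstract alone could suggest, its mean would be about 115 days. That is 115−102 = 13 to 115−81 = 34 days later than the first four CTRL calendars.

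**4. Does interval censoring remove it?** Lognormal crossing times, with true mean 41-42 days:

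| Calendar | First-test mean | Interval-censored mean |
|---|---|---|
| PENELOPE, 4-6 weeks | 58.3 | 41.5 |
| CTRL, first test 6-12 weeks | 78.5 | 41.9 |
| CTRL, first test 4-26 weeks | 113.7 | 41.5 |

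The gaps fall from 78.5−58.3 = 20.2 and 113.7−58.3 = 55.4 days to 0.4 and 0.0 days. An interval-censored Weibull mixture fitted to the first four scenarios of step 3 gave −0.4, +0.1, 0.0 and +0.3 days. Both models matched the way the data were generated, and test dates did not depend on LDL-C, so these are best cases.

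**The case against.** The strongest reply is that the protocol does not fix the first on-target test as the event date. Section 10 leaves the methods to the SAP and section 8a leaves value handling to the endpoint charter. Neither is shown, and an interval-censored analysis there could remove most of the bias. This stands against any claim that outcome a can only use the first test date. It does not clear the protocol wording: the summary measure, a mean time compared between cohorts, is set in section 8b, and timing alignment is written for b and not for a.

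Second, the size and even the direction are assumed. This also stands. A reader might infer that the outcome is sure to show a false delay of weeks in CTRL. The documents do not support that, because they give no CTRL test dates and leave open which PENELOPE values are used.

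Third, testing after each step belongs to the protocolized strategy, since the result triggers the next step. A reader might infer that outcome a measures the test calendar and nothing else. That too goes beyond the documents, since true differences in treatment timing also enter it. An interval-censored analysis aims to keep a truly earlier crossing and remove only the detection lag.

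Fourth, the remedy has limits. Test dates may depend on the LDL-C course or on treatment steps. The Turnbull estimator gives no full mean when non-reachers are right-censored. Some patients may already be at target at admission, since step 1 applies only above 1.8 mmol/L. All three points stand and shape the fix.

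Finally, this is one of five secondary outcomes, and section 3 frames the purpose as incidence at set time points. That limits the weight of the point but does not remove it.

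**Conclusion.** The point holds in conditional form. As worded, outcome a is confounded by test timing: the cohorts were tested on different calendars by design, and equal LDL-C courses with equal attainment can still give different mean times.

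With PENELOPE on its stepwise calendar, the assumed CTRL calendars give gaps from about −4 days, through 0, to +70 days. Restricting PENELOPE to three-month and one-year values could make PENELOPE look 13 to 34 days slower. All day counts are illustrative. They rest on the assumed test dates, crossing times and 70% attainment, and none predicts the actual result. The mechanism does not depend on those choices; size and sign do. The point deserves a change before analysis, and it concerns this secondary outcome only.

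**What to change.** In section 8b a), replace the plain mean with an interval-censored time-to-target comparison under the same rule in both cohorts:

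- **Lower bound:** the last LDL-C above 1.8 mmol/L, or admission if there is none.
- **Upper bound:** the first LDL-C ≤1.8 mmol/L on oral therapy.
- **Never at target:** right-censored at the last oral-only LDL-C within a common follow-up horizon. The documents name one year for PENELOPE and 18 months for CTRL. Section 10 applies its PCSK9-inhibitor rule to the primary outcome and to b, c and e, but does not list a, so state it for a as well.
- **At target at admission:** one stated rule for both cohorts.
- **Summary:** the cumulative curve (Turnbull, or a parametric model with a never-reach fraction), with a median or restricted mean. Do not report a full mean when some patients never reach target.
- **Inputs and limitation:** name the PENELOPE values used, and state that test dates may depend on the LDL-C course or treatment steps.

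The cost is protocol and SAP wording plus one analysis. CTRL already collects all available lipid values, and PENELOPE measured LDL-C after each step. The price is a somewhat wider confidence interval and a model assumption between tests.

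At minimum, and with no modelling, relabel the outcome *time to first documented on-target test*, report test dates per cohort, treat it as descriptive, and do not interpret it as speed of LDL-C lowering.

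### The second 90-day analysis of outcome b accepts an additional CTRL LDL-C with no latest date, even after a further oral drug change

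*Protocol*

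**What the plan says.** Protocol section 8b defines secondary outcome b as target attainment "within 90 days after admission for a type I (N)STEMI with oral lipid lowering medication only" and gives two ways to estimate it.

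- The first is strict. It counts attainment at least once inside the window, "without using LDL-C measurements after this window".
- The second adds, for CTRL, the "first available LDL-C measurement (at least 14 days) after the last modification in oral lipid lowering therapy within 90 days after baseline". The text makes plain that such a value counts "even if this measurement is after 90 days".

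The reason given for the second analysis is that CTRL should resemble the PENELOPE data, "where LDL measurement 4-6 weeks after a drug regimen change was mandatory to establish the treatment effect", and should include the effect of the last regimen change made by day 90.

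Four other places bear on this:

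- Section 3 describes PENELOPE timing differently: "Protocolized LLT consisted of 3 steps, with LDL-C levels measured" at least 4 weeks after each step, with no upper bound.
- Section 7 collects CTRL data "starting at admission up to 18 months". This covers all lipid panels and the start dates, stop dates and dosage of lipid-lowering drugs.
- Section 10 removes patients from outcome b once they start a PCSK9 inhibitor.
- Section 8a leaves missing and out-of-window values to an endpoint charter. That sentence stands under the primary outcome.

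**The concern.** The second analysis is the one presented as comparable to PENELOPE, and section 2 names 3 months as one of the two comparison times. Its purpose is to let the last change made by day 90 show its effect. That justifies looking somewhat beyond day 90. It does not justify an open end, and it does not justify a value taken after treatment has been changed again.

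LDL-C testing in CTRL followed routine care, whereas PENELOPE mandated a measurement after each change. Long gaps between a change and the next LDL-C are therefore to be expected mainly in CTRL. A CTRL patient whose statin was intensified or who received ezetimibe months later, and who reached target only then, can be counted as having reached it by 90 days. The effect of protocolised care at 3 months would then be measured against a control figure that contains later treatment.

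**Working it through.** The protocol states no figure for this rule, so there is nothing to reproduce. The check is day arithmetic, a comparison of sets, and an illustration on assumed shares.

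**1. Which dates the rule accepts.** Let *t* be the day of the last oral change made by day 90, with admission as day 0.

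- Earliest accepted value: *t* + 14 (section 8b).
- The 4-6 week interval cited for PENELOPE: *t* + 28 to *t* + 42 (section 8b).
- Latest value that can be in the data: 18 × 365.25 / 12 = 547.9, about day 548 (section 7).

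| Last change by day 90 (*t*) | Accepted as written | 4-6 weeks after *t* | Longest lag (548 − *t*) |
|---|---|---|---|
| 0 | 14 to 548 | 28 to 42 | 548 days |
| 30 | 44 to 548 | 58 to 72 | 518 days |
| 60 | 74 to 548 | 88 to 102 | 488 days |
| 90 | 104 to 548 | 118 to 132 | 458 days |

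For a change on day 90, the rule runs 548 − 132 = 416 days past the 6-week point.

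**2. A value that satisfies the rule but not its purpose.** Suppose the last change by day 90 is on day 60, a further statin or ezetimibe change follows on day 150, and the first LDL-C after day 74 is taken on day 200. This is the first available value at least 14 days after the day-60 change, so it is accepted. It comes 140 days after that change and 50 days after the later one.

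**3. Direction.** Compare the rule as written with the same rule plus a latest date and a bar on values after a further change. Both count every patient at target within 90 days. The additional values accepted under the capped rule are a subset of those accepted as written. With the same denominator, the attainers under the capped rule are therefore a subset of the attainers as written. The open rule can add CTRL attainers and cannot remove any.

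**4. Size, on assumptions only.** Let *f* be the share of CTRL patients who are not otherwise counted and whose additional value is accepted only because the rule is open. Let *q* be the share of those values at target. The increase in CTRL incidence is *f* × *q*. The protocol gives neither share.

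- *f* = 5%, *q* = 30%: 0.05 × 0.30 = 1.5 points.
- *f* = 10%, *q* = 50%: 0.10 × 0.50 = 5 points.
- *f* = 20%, *q* = 70%: 0.20 × 0.70 = 14 points.

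For scale, take the 663 PENELOPE patients (section 6a), 700 to 1200 CTRL patients (section 6d) and an assumed 50% attainment in both cohorts. The half-width of a 95% confidence interval for the difference is 1.96 × √(0.25/663 + 0.25/*n*), which is 5.3 points at *n* = 700 and 4.7 points at *n* = 1200.

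**The case against.** Much can be said for the plan, and several points stand.

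- **The strict analysis stands beside it.** Reporting both shows how much the values after day 90 contribute. This limits the harm. It does not repair the analysis that is offered as comparable to PENELOPE.
- **Exposure is narrower than it looks.** Only the first available value is used, so a very late one enters only if no LDL-C was taken in between. PCSK9 inhibitor starters are already excluded, so the later changes at issue are oral ones. Day 548 is an extreme.
- **The endpoint charter may set a limit.** It might. But section 8b fixes the rule itself without referring to the charter, and a rule with no upper end makes no late value out of window.
- **PENELOPE may have been open-ended too.** On the section 3 description it had no upper bound, so an open end does not by itself show that the cohorts differ. This stands, and it is why the two descriptions must be reconciled before a limit is chosen. It does not touch values taken after a further change, which defeat the rule's purpose under either description.

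A reader might also draw three stronger conclusions that the protocol does not support.

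- **CTRL is also marked down for later non-adherence.** Attainment counts if reached at least once and the value is additional, so a late off-target value removes nobody.
- **The first analysis has no valid denominator,** because it speaks of "only including patients reaching (at least once) LDL-C target within 90 days". The outcome is a cumulative incidence, and the phrase most naturally says which attainments count. Restricting the cohort to attainers would give 100%, which cannot be meant.
- **The 14-day minimum is an error.** It reads as a deliberate allowance for unscheduled care. Replacing it with 28 days is a trade-off, not a correction.

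**Conclusion.** The concern holds for the second analysis of outcome b. As written, an LDL-C that reflects oral treatment changed after day 90 can count as a 90-day attainment, up to about day 548. This runs against the stated aim of capturing the last change within 90 days and of resembling PENELOPE.

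The bias has one direction. Compared with a capped rule and with an unchanged denominator, it can only raise CTRL incidence. It would tend to shrink any PENELOPE advantage, on the expectation that mandated testing leaves few such late values in PENELOPE.

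The size is undetermined. The range of 1.5 to 14 points rests wholly on assumed shares and shows only that the effect could be small, or could exceed the sampling error of the comparison. The primary outcome and the strict 90-day analysis are not affected. The rule should be changed, but it does not put the study's main result in doubt.

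**What to change.** In section 8b, and in the endpoint charter if it governs this outcome:

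- Keep every on-target value within 90 days, as now.
- Accept the additional LDL-C after day 90 only if it precedes any further lipid-lowering change and falls no later than a stated limit after the last change made by day 90, for example 6 weeks plus a stated tolerance.
- Apply the same rule to PENELOPE.
- State that all analysed patients stay in the denominator, including those without an additional value.
- Reconcile the PENELOPE measurement timing in section 8b (4-6 weeks) with section 3 (at least 4 weeks) when choosing the limit.
- Optionally, add a sensitivity analysis with a 28-day minimum lag for the additional value.

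No new CTRL data are needed, since section 7 already collects all lipid panels and the drug dates and dosage. The cost is that fewer CTRL patients will have an additional evaluable value.
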